FV & FVIII deficiency

Combined FV & FVIII deficiency is an autosomal recessive disorder. Individuals with a FV and FVIII deficiency do not have a more severe bleeding tendency than individuals with either a FV or a FVIII deficiency [28]. Those affected usually have a mild to moderate bleeding tendency, with mucous membrane bleeding like epistaxis (19 to 77%), gum bleeding (49 to 64%), menorrhagia (66 to 100%) and post-traumatic/post-surgery (62 to 85%) as the most common manifestations [29]. Joint and muscle bleedings were reported in 25% and 7% of 27 patients in one series, but it was not reported whether these bleedings were spontaneous [23]. In the same patient series 22% reported cord bleeding and 4% central nervous system bleeding.

FVII deficiency

FVII deficiency is an autosomal recessive disorder. The clinical manifestation is heterogeneous. There is a weak correlation between the level of FVII and bleeding tendency. Mild disease will lead to easy bruising, bleeding from mucous membranes or menorrhagia [5]. Severe and homozygous FVII deficiency may lead to haemarthrosis, cerebral haemorrhage and catastrophic haemorrhage after parturition, surgery or injury [5, 30]. In a large series of 73 homozygous individuals intracranial haemorrhage (2%), gastrointestinal bleeding (17%), haemarthrosis (13%), epistaxis (58%), gum bleeding (38%), easy bruising (37%), haematoma (15%), hematuria (10%) and menorrhagia (73%) were described [31]. Interestingly, 19% of heterozygous individuals reported spontaneous bleeding, though severe spontaneous haemorrhages (intracranial and gastrointestinal) were not reported in this series [31]. In contrast, in a series of 49 patients with <10% FVII 17% reported central nervous system bleeding and 14% gastrointestinal bleeding [23].

FX deficiency

FX deficiency is an autosomal recessive disorder. The risk of bleeding correlates well with coagulation factor activity level [19]. Severe bleeding occurs in patients with factor levels below 10%, and includes umbilical cord, intracranial, joint and muscle bleeding and excessive bleeding after surgery or trauma. Heterozygous individuals can have a bleeding tendency. [32].

FXI deficiency

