1.4. Laboratory

The laboratory diagnosis of rare bleeding disorders consists of screening assays, confirmation assays, and global assays. Though characterization of the bleeding disorder is possible through this diagnostic cascade, either or not in combination with genotypic confirmation, there is no test available that sufficiently predicts bleeding phenotype. In addition, all currently available laboratory tests necessitate venepuncture. Non-invasive and/or home-based assays do not exist as yet.

Screening assays

If a bleeding disorder is suspected, clinicians will request coagulation tests and tests to exclude disorders that influence coagulation, such as thyroid disease or liver disease. A routine screening assay generally includes the following tests: activated partial thromboplastin time (APTT), prothrombin time (PT) and fibrinogen activity or thrombin time (TT); platelet function analyzer (PFA), von Willebrand factor activity and antigen, FVIII,

fibrinogen, platelet count, haemoglobin, leucocytes & differentiation, peripheral blood smear, creatinine, ALAT (alanineaminotransferase) and TSH (thyroid stimulating hormone). A prolonged aPTT or PT without another deviating test may indicate a rare bleeding disorder, if acquired diseases and anticoagulant use have been ruled out. A prolonged PT indicates a deficiency of FVII, FX, FV, FII, or fibrinogen. A prolonged aPTT indicates a deficiency of either prekallikrein, fibrinogen, FII, FV, FVIII, FIX, FXI or FXII. A prolonged aPTT and PT suggests that the abnormality is due to a deficiency in FX, FV, FII or fibrinogen.

Confirmation assays

Specific factor assays for each different coagulation factor confirm the specific rare bleeding disorder, and are necessary to give a rough indication of the level of deficiency (severe, moderate, mild). Functional assays are indicated if antigen levels are normal, slightly reduced or increased because they can confirm qualitative factor disorders. Genetic testing is not routine practice, as it does not have direct clinical implications, but may be indicated in case of preconception counselling.

Global assays

The Nijmegen Haemostasis Assay (NHA) measures thrombin and plasmin generation in a single well and allows the detection of coagulation, fibrinolysis and their interplay in a single assay [39]. Preliminary data of 41 patients suggest that the NHA can distinguish fibrinogen disorders and FII, FV, FVII, FX and FXIII deficiencies [40].

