Treatment and prophylaxis decisions require frequent venepuncture. Non-invasive testing does not exist yet, but would be extremely beneficial to patients and give way to a future perspective of home-based monitoring combined with home-based treatment. Saliva biomarkers that correlate with anticoagulation status have been identified in coumarin users in Radboud university medical center (unpublished data). RBiN will examine whether these biomarkers correlate with the clinical and laboratory phenotype in patients with rare bleeding disorders and if so, whether we can monitor treatment or rely treatment decisions on these biomarkers.

Precise, personalised treatment of the rare bleeding disorders is hampered by the lack of an adequate test that reflects patients' bleeding potential. At present, treatment decisions are based on clinical phenotype, and standard consensus-based approaches which give the most accurate indication available, but still need fine tuning. Because the Nijmegen

Hemostasis Assay (NHA) measures the key enzymes in both coagulation and fibrinolysis, it might give clinicians a more accurate idea of the haemostatic potential of their patients than currently used tests can. Ideally, this would enable tailored prophylaxis and ad hoc treatment change.

The diagnosis of a rare bleeding disorder is based upon a step-wise conventional laboratory approach as described above (1.4 Laboratory). This strategy is time consuming and expensive, due to the high number of laboratory assays that may be needed (sequentially) to establish a diagnosis. In addition, repeat testing is mandatory for many assays because they are highly variable and dependent on preanalytical and analytical factors. On the other hand, the cost of advanced molecular diagnosis such as whole exome sequencing (WES) is falling, and its practice is ever more common and developed. In addition, WES can trace more genetic abnormalities than current genetic analysis using gene panels can, thereby possibly explaining the differences in bleeding tendency in patients with rare bleeding disorders.

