3. OBJECTIVES

Our primary objectives are to:

- Describe the epidemiology, clinical presentation, bleeding score, bleeding episodes, quality of life, laboratory parameters, genetics and treatment of *homozygous* and known *heterozygous* individuals (of all ages) with rare bleeding disorders (disorders of fibrinogen, FII, FV, FV & VIII, FVII, FX, FXI, FXIII, alpha-2-antiplasmin and PAI-1 deficiency) in the Netherlands;
- Examine the relationship between the clinical and laboratory presentation (clinical and laboratory phenotype), and between phenotypes and genetics (genotype);
- Examine the relationship between quality of life, phenotype and genotype;
- ~~Validate the established factor activity levels for patients to remain without symptoms.~~

Our secondary objectives are to:

- Validate the established factor activity levels for patients to remain without symptoms.
- Compare the clinical presentation, bleeding score, quality of life and laboratory parameters of individuals with a rare bleeding disorder (disorders of fibrinogen, FII, FV, FV & VIII, FVII, FX, FXI, FXIII, alpha-2-antiplasmin and PAI-1 deficiency) to those of individuals with haemophilia A or B in cooperation with the HIN-6 investigators
- Establish a firm base for a future Dutch registry for *homozygous* and known *heterozygous* individuals with rare bleeding disorders
 - To develop a standard set of patient-reported, clinical and administrative data to be collected on a regular basis
- Liaise with the pro-RBDD study, a similar study in Italy, to work towards a pan-European study linking phenotype to genotype in individuals with rare bleeding disorders
- To assess if the NHA can distinguish mild clinical phenotypes in patients with similar factor activity levels
- To evaluate the usefulness of saliva coagulation biomarker tests in the management of patients with a rare bleeding disorder
- To examine whether age-dependent laboratory changes in factor concentrations and fibrinolysis occur in individuals with rare bleeding disorders and if so, whether they influence clinical phenotype
- To evaluate if patients with rare bleeding disorders are protected from arterial thrombosis

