7. STATISTICAL ANALYSIS

Statistical analysis will be performed by the research team at Radboud university medical center. First we describe the general outline of statistical analyses, then we discuss specific statistical procedures for the primary and secondary objectives separately, if appropriate.

In general, continuous variables will be described using standard summary statistics (e.g. mean, medians and corresponding 95% confidence interval (CI),); categorical variables will be described using frequencies and percentages with their 95% CIs. Group differences will be determined using analysis of variance (ANOVA) or Student's t-test for continuous variables and Fisher's exact test for categorical variables (Fisher-Freeman-Halton exact test for variables with more than two categories). Non-parametric tests will be used for results with non-normal distributions. Two-sided p-values smaller than 0.05 will be considered statistically significant. Because of the explorative character of this study no correction for multiple testing will be applied.

The following parameters will be categorized when appropriate:

- Bleeding score (ISTH-BAT): ≥ 5 abnormal for women, ≥ 3 abnormal for men
- Clinical bleeding severity [19]:
 - Asymptomatic: no documented bleeding episodes
 - Grade I bleeding: bleeding that occurred after trauma or drug ingestion (antiplatelet or anticoagulation therapy)
 - Grade II bleeding: spontaneous minor bleeding (bruising, ecchymoses, minor wounds, oral cavity bleeding, epistaxis and menorrhagia)
 - Grade III bleeding: spontaneous major bleeding (intramuscular haematomas requiring hospitalizations, haemarthrosis, bleeding of the central nervous system, the umbilical cord or the gastrointestinal tract)

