7.2. Secondary objectives

- *Compare the clinical presentation, bleeding score, quality of life and laboratory parameters of individuals with a rare bleeding disorder (disorders of fibrinogen, FII, FV, FV & VIII, FVII, FX, FXI, FXIII and alpha-2-antiplasmin and PAI-1 deficiency) to those of individuals with haemophilia A or B (HiN study data will be shared)*
Descriptive statistics will be used. Group differences will be determined using the statistics as described in Statistical Analysis above.
- *Establish a firm base for a future Dutch registry for homozygous and known heterozygous individuals with rare bleeding disorders (disorders of fibrinogen, FII, FV, FV & FVIII, FVII, FX, FXI, d FXIII and alpha-2-antiplasmin and PAI-1 deficiency):*
 - *To develop a standard set of patient-reported, clinical and administrative data to be collected on a regular basis*

No statistics are involved in this objective.

- *Liaise with the pro-RBDD study, a similar study in Italy, to work towards a pan-European study linking phenotype to genotype in individuals with rare bleeding disorders*
No statistics are involved in this objective.
- *To assess if the NHA can distinguish mild clinical phenotypes in patients with similar factor activity levels*
We will calculate diagnostic accuracy comparing NHA to ISTH BAT.
- *To evaluate the usefulness of saliva coagulation biomarker tests in the management of patients with a rare bleeding disorder*
Descriptive statistics will be used. Regression analysis will be used to determine the association between saliva biomarker tests (dependent variable) and coagulation factor activity level as a continuous variable (independent variable), with adjustment for age at data collection, sex, etcetera.

- *To evaluate the use of WES in explaining differences in bleeding tendency.*
Descriptive statistics will be used.
- *To examine whether age-dependent laboratory changes in factor concentrations and fibrinolysis occur individuals with rare bleeding disorders? And if so, do they influence clinical phenotype?*
Descriptive statistics will be used. Regression analysis will be used to determine the association between age (dependent variable) and coagulation factor activity level as a continuous variable (independent variable), with adjustment for age at data collection, sex, etcetera.
- *To evaluate if patients with rare bleeding disorders are protected from arterial thrombosis*

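### The NHA objective asks about discrimination at similar factor levels, but the stated accuracy analysis does not condition on factor level or disorder

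*Combined protocol and SAP*

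**What the plan says.** Sections 3 and 7.2 word the objective identically: "To assess if the NHA can distinguish mild clinical phenotypes in patients with similar factor activity levels". The analysis given for it in section 7.2 is a single sentence: "We will calculate diagnostic accuracy comparing NHA to ISTH BAT". No NHA parameter or NHA cut-off is named, and nothing says what counts as a similar level.

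Section 7 supplies the cut-off for the reference, "Bleeding score (ISTH-BAT): ≥ 5 abnormal for women, ≥ 3 abnormal for men", together with general summary statistics and group tests. It has no rule for restricting, stratifying or adjusting by factor level. Other objectives do get covariates. The saliva biomarker objective, for example, is to be analysed by regression "with adjustment for age at data collection, sex, etcetera". The NHA objective gets none.

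Section 2 explains the interest in the assay: "it might give clinicians a more accurate idea of the haemostatic potential of their patients than currently used tests can".

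**The concern.** The objective is about added information: given the factor level, does the NHA tell mild from other phenotypes? Accuracy of the NHA against ISTH-BAT answers a different question, namely whether the NHA is related to bleeding at all, by any route.

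The protocol itself describes two indirect routes. First, bleeding follows factor level in at least one disorder; of FX deficiency, section 1.2 says "The risk of bleeding correlates well with coagulation factor activity level". If the NHA also follows factor level, the two will be associated even when the NHA adds nothing. Second, the NHA appears to separate disorders, as section 1.4 reports: "Preliminary data of 41 patients suggest that the NHA can distinguish fibrinogen disorders and FII, FV, FVII, FX and FXIII deficiencies". Section 1.2 shows that the level needed to stay asymptomatic differs by disorder, from 12% for FV to 56% for FX. An analysis that pools disorders can therefore pick up the type of disorder as well as the level.

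At stake is the reading of the result. An AUC clearly above 0.5 could be reported as a yes to the objective when the correct answer is that the assay adds nothing at a given level.

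**Working it through.** The plan gives no sample size, target accuracy or expected AUC for this objective, so there is no figure to reproduce. The check asks what the stated calculation returns for an NHA that, by construction, carries only factor level plus noise.

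**Inputs from the documents**
- Known patients: 337 (section 5.1, Table 3). Expected response: 70% (section 5.1). 0.70 × 337 ≈ 236 participants.
- About one third of known patients are minors (section 8.4). 236 × 2/3 ≈ 157 adults.
- Section 2 calls the link between level and bleeding weak or absent for FV, FVII and FXI. Table 3 counts 22 + 92 + 88 = 202 of 337, or 60%. FX has 10 known patients.

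**Assumed inputs (the documents give none)**
- Factor level F is standard normal.
- Model A: log-odds of an abnormal ISTH-BAT = −b × F; NHA = F + noise with SD 0.3 or 0.6. The correlation of NHA with F is 1/√(1 + SD²), so 0.96 or 0.86.
- Model B: latent bleeding score correlated −r with F; NHA correlated q with F; 30%, 50% or 70% abnormal.

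**Results, model A** (400,000 draws per scenario)

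| b per SD of level | Crude AUC | AUC within 200 narrow level bands |
|---|---|---|
| 0.25 | 0.56–0.57 | 0.50 |
| 0.5 | 0.62–0.63 | 0.50 |
| 1.0 | 0.71–0.73 | 0.50 |
| 1.5 | 0.77–0.80 | 0.50 |
| 2.5 | 0.83–0.88 | 0.50 |

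**Results, model B** (50% abnormal; 400,000 draws per scenario)

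| r | Crude AUC, q = 0.6 | Crude AUC, q = 0.9 | Within-level AUC |
|---|---|---|---|
| 0 | 0.50 | 0.50 | 0.50 |
| 0.2 | 0.55 | 0.58 | 0.50 |
| 0.3 | 0.58 | 0.62 | 0.50 |
| 0.5 | 0.64 | 0.71 | 0.50 |
| 0.7 | 0.69 | 0.79 | 0.50 |

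With 30% or 70% abnormal, the crude values move by about 0.01. Where the NHA follows level only loosely (q = 0.6), even a strong link gives 0.64 to 0.70, below the upper range from model A.

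**Would this look like a finding?** With the Hanley–McNeil standard error at n = 236, half abnormal and AUC 0.583 (r = 0.2, q = 0.9), the SE is 0.037 and the 95% CI is 0.583 ± 1.96 × 0.037 = 0.51 to 0.66. For adults only, the SE grows by √(236/157) = 1.23 to about 0.045, and the interval becomes 0.49 to 0.67. At r = 0.3, q = 0.9 (AUC 0.62), the interval at n = 236 is 0.55 to 0.69. A weak link is thus borderline for a spurious positive, and a moderate one would usually produce it.

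**Expected adults per disorder** (known × 0.70 × 2/3): FVII 43, FXI 41, PAI-1 18, alpha-2-antiplasmin 14, fibrinogen 13, FV 10, FXIII 7, FX 5, FII 4, FV & VIII 2. This limits which models can be fitted.

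**The case against.** The strongest reply is that the method sentence sits directly under an objective that already names the population. On that reading the accuracy calculation is restricted to patients with similar levels, and the plan has only left out the detail. This may be what the authors meant. A reader might infer that the plan commits to an unrestricted analysis; the text does not say that. But it also does not say what similar means, how patients would be grouped, or how ten disorders with different level scales would be combined. The sentence as it stands therefore cannot be carried out as a conditional analysis.

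A second reply is that the protocol's own account makes the bias small for most patients. This stands in part. A reader might infer that accuracy against ISTH-BAT would mostly re-measure factor level. The documents do not support that: the link is described as weak or absent for 60% of known patients, and with no link the crude AUC is 0.50. The preliminary NHA data also do not list FXI (88), PAI-1 (39) or alpha-2-antiplasmin (29), together 156 of 337, so the NHA's dependence on the missing factor is not shown there. The upper range of AUC belongs to disorders with a strong link.

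A third reply concerns children. The cut-offs, "≥ 5 abnormal for women, ≥ 3 abnormal for men", might suggest that the reference is simply undefined for the third of patients who are minors. Table 4 in section 6.1 assigns children a separate instrument, iCHEC, so the ISTH-BAT sentence can be read as covering adults. What is missing is an NHA analysis for children, which is a smaller point.

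**Conclusion.** The concern holds in limited form. The objective is conditional on factor level, the stated method is not, and nothing in section 7 supplies the condition. Calculated as stated, an NHA with no information beyond factor level gives a crude AUC of about 0.55 to 0.63 under a weak link. Under a strong link and an NHA that tracks level closely, it gives about 0.70 to 0.88. At a fixed level it gives 0.50. These ranges rest on assumed links between level, NHA and bleeding. They treat patients as one group, and pooling disorders could add to them.

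It would go too far to conclude that the NHA is uninformative or that a high AUC would necessarily be spurious. The point is that the planned number cannot tell the two apart. The objective is secondary, the study is declared exploratory, and no primary objective is affected. The change should be made, but it is not critical to the study.

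**What to change.** Replace the sentence in section 7.2 with an added-value analysis:

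- **Main analysis, adults.** Logistic model of abnormal ISTH-BAT on the level of the deficient factor (expressed per disorder), a disorder term, age and sex, fitted with and without one or two NHA parameters named in advance. Report the change in AUC with its 95% CI. The smallest disorders will need to share a category in the disorder term.
- **Direct answer to the objective.** NHA accuracy within factor-level bands defined before the data are seen, so that similar levels has a stated meaning.
- **Within-disorder models** only for FVII and FXI, with about 40 expected adults each, and with few terms, for example level plus one NHA parameter. Describe the other disorders.
- **Overall accuracy** of the NHA against ISTH-BAT kept as description, not as the answer.
- **Children** analysed separately against iCHEC.

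Table 4 already schedules the factor and fibrinolysis assays alongside the NHA, so no new data are needed. The cost is revised wording and a little more analysis. The estimate will be less precise than the crude one and probably less favourable to the assay; with about 157 expected adults, a wide interval should be expected and reported as such.

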TSH	Thyroid Stimulating Hormone
VWF	Von Willebrand Factor
Wbp	Personal Data Protection Act (in Dutch: Wet Bescherming Persoonsgegevens)
WES	Whole Exome Sequencing
WMO	Medical Research Involving Human Subjects Act (in Dutch: Wet Medisch-wetenschappelijk Onderzoek met Mensen)

SUMMARY

Rationale: Rare bleeding disorders (deficiency of fibrinogen, factor II, V, V&VIII, VII, X, XI, XIII, α 2-antiplasmin or plasminogen activator inhibitor 1) are not well defined with respect to their clinical phenotype, laboratory phenotype en genotype. At present, little is known about their clinical presentation, bleeding scores, bleeding episodes, health-related quality of life, laboratory parameters, genetics and current treatment. There are large differences in bleeding tendency and weak correlations with the level of factor deficiencies. Therefore, it is essential to perform thorough research in patients with rare bleeding disorders and perform laboratory and genetic tests, to seek explanations for the variety in clinical phenotype.

Objective: The purpose of the RBiN study is to describe the epidemiology, bleeding tendency, laboratory parameters, quality of life and genetics of all known patients in the Netherlands with rare bleeding disorders. In addition, the study aims to examine the relationship between clinical phenotype, laboratory phenotype and genotype.

Study design: cross-sectional multicenter observational study.

Study population: all patients registered in Dutch Haemophilia Treatment Centers with known disorders of the coagulation factors fibrinogen, factor II, V, V & VIII, VII, X, XI, XIII, α 2-antiplasmin and plasminogen activator inhibitor type 1, aged 1 years and older.

Main study parameters/endpoints:

Description of the clinical phenotype, laboratory phenotype, genotype and quality of life.

Nature and extent of the burden and risks associated with participation, benefit and group relatedness: participating patients will be invited for one visit to their treatment center in order to draw blood, take a saliva sample and perform questionnaires. This will take approximately 40 to 120 minutes. Since the population of patients with RBDs is very small it is important to include all patients, also minors (children <18 years), in the study (around one third of known patients are minors). Therefore, this study may be regarded as group-related. The risk associated with participation is negligible.

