In adults and children ≥ 12 years old, roughly 67 ml blood will be drawn through a study-related venepuncture. Forty-seven ml of this sample will be used for this study while the remaining 20 ml will be stored in the Radboud university medical center Biobank for future research. Additional information about the Biobank is provided in separate documents.

Blood samples will be used for the experiments specified in table 4.

In children under 16 years of age, whole exome sequencing will not be performed. Also, the following tests are not performed under 12 years of age: ALAT, TSH, creatinine, lupus anticoagulans and d-dimer. Therefore, only 47mL of blood will be needed for these children. For children under 8 years of age, in addition there will be no blood drawn for the biobank so that they only need to supply 27mL of blood.

Remaining material can be used for future research. In this case, studies will be performed according to the protocol Biobank Hematologie HEMBB (IRB Registration number: CMO Arnhem-Nijmegen 2013/064). In case the research would not be within the scope of HEMBB, the CMO will be consulted in advance.

Saliva sampling

Whole saliva will be collected in the morning when patients did not drink more than 2 glasses of alcohol on the evening before and did not eat 1 hour before collection. In case of infections

in the oral cavity or a severe cold, patients will be excluded. Before saliva collection the mouth will be rinsed with water and donors will be allowed to chew on 25 cm² sheet of parafilm (Parafilm® M) for 1 minute. Produced saliva will be collected into a 50 ml tube and centrifuged at 10,000g for 10 minutes. Samples will be divided in aliquots of 250 µl and stored at -80°C. Stimulated whole saliva collection will be used because of its non-invasive approach instead of e.g. glandular saliva donation, and since stimulated whole saliva has been found to have a large portion of peptides and proteins derived from the parotid glands. Specimens will be processed with several techniques including ELISA and proteomics.

Saliva samples are only collected in patients ≥4 years old.

Electronic patient records

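### The saliva objective asks about usefulness in patient management, but the planned regression on factor level, from one sample per patient, cannot answer that question

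*Combined protocol and SAP*

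**What the plan says.** Section 3 gives the secondary objective as: "To evaluate the usefulness of saliva coagulation biomarker tests in the management of patients with a rare bleeding disorder". Section 2 (Rationale) starts from saliva markers identified in coumarin users. It says the study will examine whether they correlate with both the clinical and the laboratory phenotype and, if they do, "whether we can monitor treatment or rely treatment decisions on these biomarkers".

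Section 7.2 plans descriptive statistics and one inferential analysis: "Regression analysis will be used to determine the association between saliva biomarker tests (dependent variable) and coagulation factor activity level as a continuous" independent variable, "with adjustment for age at data collection, sex, etcetera". The bullet just before it, on the Nijmegen Haemostasis Assay (NHA), plans diagnostic accuracy against the ISTH-BAT. The saliva bullet plans nothing of that kind.

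Sampling and general rules:

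- The Summary says patients are "invited for one visit to their treatment center in order to draw blood, take a saliva sample" and complete questionnaires. Section 6.5 says the study has no follow-up.
- Section 6.2 limits saliva to patients aged 4 and over and adds: "Specimens will be processed with several techniques including ELISA and proteomics". The number of markers is not given.
- Section 7 sets the rule "Two-sided p-values smaller than 0.05 will be considered statistically significant" and adds: "Because of the explorative character of this study no correction for multiple testing will be applied".

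**The concern.** A test helps in management if it tells the clinician something accurate enough about the individual patient. For monitoring, it must also follow that patient's changes over time. An average slope across patients establishes neither. Three things are missing.

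1. There is no individual-level performance measure: no discrimination, cut-off, prediction error or criterion of usefulness. The model also has the marker as outcome, whereas a clinician would want factor level or bleeding tendency predicted from the marker.
2. The Rationale announces the relation to clinical phenotype, but section 7.2 has no saliva analysis for it.
3. One sample per patient gives no information on within-patient change.

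The study could follow its plan exactly and still leave its saliva question unanswered. If many proteins are screened without correction, it could also produce chance leads for a non-invasive test.

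**Working it through.** The documents give no sample size, effect size or performance target for saliva, so there is no design figure to reproduce. The check asks how weak an association can be and still pass the only inferential test.

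**Inputs.** Known patients by disorder (Table 3): 28 + 9 + 22 + 4 + 92 + 10 + 88 + 16 + 39 + 29 = 337, which agrees with the stated total. Expected response is 70% (section 5.1), so 337 × 0.70 = 236. The saliva number will be lower because of the age limit; 200 is used as an assumed lower value. Alpha is 0.05, two-sided.

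**Smallest significant partial correlation.** |r| = t / √(df + t²), with t the 97.5% point on df = n − 2 − 2 degrees of freedom. The last 2 stands for age and sex; further covariates are not named.

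Pooled over disorders (an assumption; section 7.2 does not say):

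- n = 236: df = 232, t = 1.970, |r| = 0.128, R² = 1.6%.
- n = 200: df = 196, t = 1.972, |r| = 0.139, R² = 1.9%.

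Within disorder, at 70% of the Table 3 counts:

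| Disorder | n | Smallest significant \|r\| |
|---|---|---|
| FVII | 64 | 0.25 |
| FXI | 62 | 0.25 |
| PAI-1 | 27 | 0.40 |
| Fibrinogen | 20 | 0.47 |
| Alpha-2-antiplasmin | 20 | 0.47 |
| FV | 15 | 0.55 |
| FXIII | 11 | 0.67 |
| FX | 7 | 0.88 |
| FII | 6 | 0.95 |
| FV & VIII | 3 | cannot be fitted |

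**What such a correlation means for one patient.** The share of the SD left unexplained is √(1 − r²). The AUC for telling the lower from the upper half of factor levels was simulated under an assumed bivariate normal model.

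| r | Residual SD / raw SD | AUC |
|---|---|---|
| 0.128 | 0.99 | 0.56 |
| 0.139 | 0.99 | 0.56 |
| 0.25 | 0.97 | 0.61 |
| 0.30 | 0.95 | 0.64 |
| 0.50 | 0.87 | 0.73 |

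Taking the lowest third or fifth as the low group instead of the lower half raises the AUC by no more than about 0.02.

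**Direction of the regression.** With one marker and the same covariates, exchanging outcome and predictor leaves the partial correlation and the p-value unchanged. It does change what is estimated: the error in predicting factor level comes only from the model with factor level as outcome.

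**Chance findings.** Expected null markers passing = 0.05 × number tested: 1 of 20, or 5 of 100. With independent markers, the chance of at least one is 1 − 0.95^k: 23% for k = 5, 64% for k = 20, 99% for k = 100. All these values of k are assumptions. Correction alone does not solve the main problem. With Bonferroni over 20 markers at n = 236 the threshold is |r| = 0.197, still only R² = 3.9%.

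**The case against.** The case on the other side is substantial.

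- **A reader might infer that weak or chance markers will be declared useful.** The documents do not support this. Section 7 calls p < 0.05 statistically significant and no more; the plan has no criterion of usefulness, good or bad.
- **The plan is not only a p-value.** It includes descriptive statistics, and a fitted regression yields a slope, R² and residual SD. This is fair, but none of these is named as a result to be judged, and with the marker as outcome the residual SD is that of the marker.
- **A reader might infer that trivially weak associations will generally pass.** That holds only if ten disorders are pooled. Each has its own deficient factor, and section 1.2 lists fibrinogen in other units. Within disorders the threshold is 0.25 or more. This stands as a limit on the pooled figures.
- **A reader might infer a large count of false-positive proteins.** No number of markers is given, the Rationale begins from markers already identified, and section 7.2 does not say that every quantified protein is tested. Only the 5% rate can be stated.
- **Lack of correction is disclosed and justified as exploratory**, for a secondary objective. That can excuse an uncorrected screen; it sits poorly with an objective about management.
- **The Rationale does not claim that monitoring works.** It poses the question conditionally. That is right, but the design still cannot answer it.

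The objection removes the stronger readings. It does not supply a performance measure, a clinical-phenotype analysis or repeated samples.

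**Conclusion.** The concern holds as a mismatch between objective and analysis. A significant slope could not show usefulness in management, and one sample per patient cannot inform monitoring. The announced link to clinical phenotype has no saliva analysis, although accuracy is planned for the NHA in the same section.

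The size depends on how disorders are handled. If pooled at n about 200 to 236, |r| of 0.13 to 0.14 passes with R² under 2% and an AUC of about 0.56. Within FVII or FXI the threshold of about 0.25 still means an AUC of only about 0.61. In the smaller groups the greater risk is missing real associations. These figures assume 70% response, adjustment for age and sex only, and bivariate normality for the AUC. If many proteins are tested, about 5% of the null ones would pass. This is a secondary, exploratory objective, but the change is cheap and should be made.

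**What to change.** 1. **Objective (sections 3 and 7.2).** Restate it as cross-sectional association and discrimination. State that monitoring and treatment decisions, raised in section 2, cannot be assessed in this study.
2. **Clinical phenotype.** Add the AUC with 95% CI for an abnormal ISTH-BAT score, using the section 7 cut-offs. These are given for women and men only and Table 4 names a different tool for children, so say how children are handled.
3. **Factor level.** Make it the outcome, predicted from the marker. Report R² and cross-validated prediction error with intervals, stratified by or adjusted for disorder. Give separate estimates only in the larger groups, such as FVII and FXI.
4. **AUC against a factor-level cut-off.** Keep this secondary and restrict it to disorders with an asymptomatic level listed in section 1.2. None is listed for FII, PAI-1 or alpha-2-antiplasmin: 9 + 39 + 29 = 77 of 337 known patients (23%). The listed levels are themselves to be validated in this study.
5. **Markers.** Name the markers already identified in coumarin users as the pre-specified set. Label other proteomic results as discovery, at a stated false discovery rate.

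The cost is revised wording and a little more analysis, with no extra visits or samples. The downside is a more modest claim and wide intervals in the small disorders.
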